The reasons for underutilization of appropriate GDMT in HF are multifactorial. In the Indian Health Service, access to cardiology care is severely limited, and HF care is provided primarily by primary care providers. We surveyed primary providers at two Indian Health Service sites to identify the primary barriers to getting HFrEF patients on appropriate GDMT. The primary barriers identified were include lack of knowledge/comfort among providers about guidelines and appropriate management, clinical burden, time constraints during the visit. Given this we hypothesized that a model that identified HFrEF patients not on appropriate therapy, and initiated missing recommended therapy by the study team would be an effective way to improve HF quality of care and uptake of GDMT. In addition, given the rurality of the Navajo patients cared for at these two IHS sites, and the barriers to accessing care, we hypothesized that a telemonitoring model in which patients had GDMT initiation and uptitration at home, with home BP monitoring would be preferable.

We therefore, in discussion with community members and primary providers at two IHS sites in Navajo, designed a model to identify HFrEF patients cared for in the system, identify gaps in their therapy, and initiate appropriate therapy by the study team with home BP and HR monitoring for initiation and titration of GDMT. We propose a stepped wedge randomized trial to compare the implementation of this model compared to usual care over a 6 month period with 5, 30-day cross over periods. The primary outcome for the trial will be the proportion of patients who have an increase in the number of prescribed evidence-based therapies for HFrEF (beta-blockers, ACE-I/ARB/ARNI, MRA, SGLT2i) 30 days post implementation. This endpoint is based on filling of the prescription. In addition to addition of missing GDMT, we will also consider a change from an ACEI/ARB to an ARNI consistent with increase in the ‘number’ of GDMT given their demonstrated benefit. Secondary outcomes will include: percentage of

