4. STUDY DESIGN

4.1 Study Overview

This is a single ‘center’ (Gallup Service Unit- which includes two ambulatory clinics), stepped wedge cluster randomized design with 5 clusters planned. We will randomize each patient to 1 of 5 clusters, each of which has a different enrollment time point, separated 1 month apart. Each patient will receive intervention with the heart failure care delivery model at time of enrollment. Evaluations will be taken at each cross-over time point and at conclusion of 6 months. Screening data will be reviewed to determine subject eligibility. Subjects who meet all inclusion criteria and none of the exclusion criteria will be entered into the study. Prior to enrollment for each patient, a message will be sent in that patient’s chart through the EHR to the patient’s primary provider who has 7 days to opt out if they think patient should not be enrolled.

Probable Duration of Project: Total duration of subject participation will be 6 months.

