4.3 Study Design

Stepped-wedge designs are increasingly being utilized to evaluate interventions within routine care and are recommended where there are limited numbers of clusters [13]. In this study, we will perform a prospective stepped-wedge randomized control trial, where randomization will occur at the patient level with 5 patient clusters.

The randomization procedures will be managed independently at the University of Pennsylvania Cardiovascular Outcomes, Quality, and Evaluative Research Center. Physicians will be randomized through a SAS-based computer-generated randomization scheme developed by the study PI. Using a stepped-wedge design, each patient cluster will begin the study as a control

site, providing treatment as usual to participants (Control). Clusters will then progressively commence the heart failure care delivery model and will begin contributing to the intervention arm of the study in a stepped fashion (Intervention; see **Figure 1**). An independent statistician at University of Pennsylvania Cardiovascular Outcomes, Quality, and Evaluative Research Center will randomly generate the clusters and the order of the patient cluster. CONSORT procedures will be followed including using an intention to treat analysis.

Figure 1: Stepped-Wedge Implementation of HF Care Delivery Model

Stepped Wedge Design

[figure not shown]

Figure 1. Stepped wedge randomized controlled study design. Participants in the control condition will receive treatment as usual. Participants in the intervention condition will receive the heart failure care delivery model as described below. The patient clusters and order of intervention will be randomly allocated.

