4.4. Randomization

Randomization in this study will occur at the level of the patient. This is a stepped wedge trial design, and patients will be randomized to 1 of 5 clusters. Every cluster will have the model implemented, but the time point of implementation will vary based on cluster, in 30 day increments. Cluster 1 will have the model implemented at time 0, cluster 2 at 30 days, cluster 3 at 60 days, etc (as shown in Figure 1). Prior to implementation, patients in pre-implementation time points will receive usual care. In addition, all providers received a lecture regarding updated ACC/AHA/HFSA guidelines and expert consensus prior to implementation of the model. Given the stepped-wedge design, all patients will eventually benefit from implementation of the model, but it also allows us to evaluate the effect of secular trends towards better care over time (and ensure the model rather than trends in care are not responsible for improving care).

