10.2.1. Serious Adverse Experience Reporting

The study team will document all SAEs that occur (whether or not related to implementation) per Penn CER guidelines. The collection period for all SAEs will begin after the first patient cluster has enrolled and end 3 months post study period.

In accordance with the standard operating procedures and policies of the local Institutional Review Board (IRB)/Independent Ethics Committee (IEC), the site investigator will report SAEs to the Navajo Nation Human Research Review Board.

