11.3. Analysis of Primary and Secondary Endpoints

To assess the effectiveness of our intervention, measurement of rates of GDMT, including each specific medication of ACE inhibitors, ARB, ARNI, beta-blockers, MRA, SGLT2 inhibitors will be performed at baseline, at each cross-over time point. The main analysis of our stepped wedge design will be based on a logistic mixed-effects model which will contain a random intercept to account for between-cluster variability, a fixed effect parameter for time, and a group indicator variable for the treatment for each subject and time to capture treatment differences over time.

Safety and tolerability data will be summarized by intervention group.

Adverse event rates will be coded by body system and MedDra classification term. Adverse events will be tabulated by treatment group and will include the number of patients for whom the event occurred, the rate of occurrence, and the severity and relationship to newly started therapy.

Statistical Analysis: The primary analysis will utilize the intention to treat principle. A generalized linear model will be used to assess the relationship between randomization cluster status and the primary outcome. The model will use a log-link and independent correlation structure to allow for calculation of adjusted risk ratios. Statistical significance will be based on a P value of <0.05. For categorical secondary outcomes, a similar generalized linear modeling approach will be used. For continuous secondary outcomes, a generalized linear model will be used.

Assessment of contamination: Providers may learn to better treat heart failure as consistent with evidence-based therapies over time. Given we are not clustering by provider, but rather patients, it is possible that providers will take what is being implemented on their patient that is in an active implementation phase, and apply it to a patient in a non-active implementation phase. Therefore, there is a high risk of contamination. However, with the stepped wedge design, we will be able to also see how GDMT rates increase over the study period for those clusters who are not immediately in an active implementation arm. We will be able to better understand if increases in GDMT are related to the intervention or just due to increases over time due to improved knowledge of providers over time.

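### The adverse event table in 11.3 leaves its rate denominator undefined and does not split patient time at crossover, so unequal exposure could read as harm, most clearly for serious adverse events

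*Combined protocol and SAP*

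**What the plan says.** On safety summaries, section 11.3 states: "Adverse events will be tabulated by treatment group". The table "will include the number of patients for whom the event occurred, the rate of occurrence", together with severity and relationship to the new therapy. The rate has no stated denominator. No section says how one patient's control and intervention time is divided for safety, or to which condition an event belongs.

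The design makes this matter. Section 4.1: "We will randomize each patient to 1 of 5 clusters". Section 4.4: "Every cluster will have the model implemented, but the time point of implementation will vary based on cluster, in 30 day increments", and then "Cluster 1 will have the model implemented at time 0, cluster 2 at 30 days, cluster 3 at 60 days, etc". On that schedule clusters 2 to 5 contribute to both conditions and cluster 1 to intervention only.

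Other parts of the document imply different exposure:
- Section 4.3 says that "each patient cluster will begin the study as a control" site, which would give cluster 1 control time as well.
- Section 11.4 bases power on four clusters and five time points including a baseline.
- Section 1 describes a comparison "over a 6 month period with 5, 30-day cross over periods". The synopsis analysis plan instead places the last measurement six months after implementation.

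Adverse events are captured throughout the study (9.1.4, Adverse Events). SAE collection alone is to "begin after the first patient cluster has enrolled and end 3 months post study period" (10.2.1).

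**The concern.** In a parallel-group trial with equal follow-up, patients with an event per arm is a fair summary. In a stepped wedge the two conditions are observed for different lengths of time, and most patients appear in both. A condition watched for longer collects more patients with events even when the risk per month is the same. Here the extra time, including the whole SAE tail, falls on the intervention side.

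The safety comparison carries weight in this trial. The protocol describes the study as minimal risk (2.1) and requests a waiver of patient consent (6.3). SAEs include death and inpatient hospitalization (10.2). A table that shows harm because of longer observation could mislead. So could a real signal that is dismissed as that artefact.

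**Working it through.** The plan states no exposure or adverse event figure, so there is nothing of its own to reproduce first.

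**Step 1: exposure in cluster-months (one month = 30 days)**

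Inputs: crossover at months 0, 1, 2, 3, 4 (4.4); study length 6 months (sections 1 and 4.1); SAE tail of 3 months (10.2.1), which is all intervention time because every cluster has crossed over by then. For 4.3, I add one control month for every cluster, so crossover is at months 1 to 5. For 11.4, I read the five time points as five one-month periods.

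| Reading | Control | Intervention | Ratio |
|---|---|---|---|
| 4.4, to month 6 | 0+1+2+3+4 = 10 | 6+5+4+3+2 = 20 | 2.0 |
| 4.4, six months after each implementation | 10 | 5×6 = 30 | 3.0 |
| 4.4, SAEs with tail after month 6 | 10 | 20+5×3 = 35 | 3.5 |
| 4.3, to month 6 | 1+2+3+4+5 = 15 | 5+4+3+2+1 = 15 | 1.0 |
| 4.3, SAEs with tail | 15 | 15+5×3 = 30 | 2.0 |
| 11.4, four clusters | 1+2+3+4 = 10 | 4+3+2+1 = 10 | 1.0 |
| 11.4, SAEs with tail | 10 | 10+4×3 = 22 | 2.2 |

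**Step 2: what equal risk would look like on the 4.4 schedule**

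Assumptions: 20 patients per cluster (11.4) in five clusters; the same constant hazard h in both conditions. The documents give no hazard, so h = 1%, 2% and 5% per month are illustrative. The expected percentage with an event is the mean over contributing clusters of 1 − exp(−h × months). Control has 80 contributing patients (clusters 2 to 5) and intervention has 100.

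At h = 2%:
- Control, months 1, 2, 3, 4: (1.98 + 3.92 + 5.82 + 7.69)/4 = 4.9%, or 3.9 patients.
- Intervention to month 6, months 6, 5, 4, 3, 2: (11.31 + 9.52 + 7.69 + 5.82 + 3.92)/5 = 7.7%, or 7.7 patients.
- Intervention with the tail, months 9, 8, 7, 6, 5: (16.47 + 14.79 + 13.06 + 11.31 + 9.52)/5 = 13.0%, or 13.0 patients.

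| h per month | Control | Intervention to month 6 | Ratio | Intervention with tail | Ratio |
|---|---|---|---|---|---|
| 1% | 2.5% | 3.9% | 1.59 | 6.8% | 2.74 |
| 2% | 4.9% | 7.7% | 1.58 | 13.0% | 2.68 |
| 5% | 11.6% | 17.9% | 1.54 | 29.4% | 2.53 |

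These ratios are smaller than the exposure ratios mainly because 80 patients contribute control time and 100 contribute intervention time. With follow-up of six months after implementation, the percentage ratios are 2.2 to 2.4. With the SAE tail on the other layouts, they are 1.9 to 2.0 (4.3) and 2.1 to 2.2 (11.4).

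**Step 3: after exposure adjustment**

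On 4.4 the denominators are 10×20 = 200 control patient-months, against 20×20 = 400 intervention patient-months to month 6, or 35×20 = 700 with the tail. Under equal risk at 2% per month, both conditions show 2 events per 100 patient-months, a rate ratio of 1.0.

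**The case against.** The strongest reply is that the plan already lists a rate beside the patient count. If that rate is per unit of patient time, its column is unbiased by exposure. This stands: a reader might infer that the plan reports patient counts only, and the text does not support that. The defect is an undefined denominator. Nothing settles it as person-time, however, and the count column is affected either way.

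A reader might also infer that exposure differs by a fixed factor of up to 3.5 for all adverse events. The documents do not support that either. The 3-month tail is written for SAEs only, 11.3 does not say whether it enters the comparison, and 4.3 and 11.4 give a ratio of 1.0 within the study.

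Other points on that side also hold:
- The tabulation is descriptive and includes relationship to therapy. Adverse events are also secondary safety endpoints (5.3), and 11.3 assigns categorical secondary outcomes to a generalized linear model, though it states no exposure offset.
- The scheduled safety look comes 30 days after cluster 1 starts. On the 4.4 schedule every patient then has 30 days in a single condition, so that look is not distorted by exposure.
- Nothing says heart failure hospitalizations as an efficacy outcome will be summarized like the adverse event table. Section 5.2 measures them at each time point.
- Section 11 promises a detailed SAP. That makes the change easy; it does not supply the definition.

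**Conclusion.** The point holds as a gap in specification with a foreseeable direction of error. As written, the patient counts, and the rate if it is a simple percentage, compare conditions observed for different lengths of time.

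For adverse events within the study, the size depends on which schedule is meant: exposure ratio 2.0 on 4.4 (3.0 with six months after implementation), but 1.0 on 4.3 to month 6 or on the 11.4 layout. For SAEs with the tail tabulated, intervention exposure is at least twice control on each of these schedules (3.5, 2.0 and 2.2). The apparent percentage ratios of 1.5 to 1.6 and 2.5 to 2.7 apply to 4.4 only. They assume 20 patients per cluster and a constant, equal hazard of 1% to 5% per month. The primary endpoint is not affected. The change should be made before the SAP is finalized.

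**What to change.** In section 11.3:
- Define the rate as events, and separately first events, per 100 patient-months in each condition. Split exposure at each patient's crossover and assign each event to the condition at its onset.
- Report patient-months and the number of patients contributing beside the counts.
- State one cut-off for adverse events and SAEs in the between-condition table, and list SAEs from the 3-month post-study tail separately as intervention-only.
- Reconcile the schedules in 4.3, 4.4 and 11.4, and say whether follow-up ends at month 6 of the study or six months after implementation.

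A comparison limited to the calendar period in which both conditions are observed can be an optional sensitivity analysis. On 4.4 that is days 0 to 120, with 4+3+2+1+0 = 10 intervention and 10 control cluster-months. It discards half of the 20 intervention cluster-months and is balanced in this way only on that schedule, so it should not replace the main table.

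The cost is SAP wording and slightly more programming; event start dates are already recorded (9.1.4, Adverse Events). Person-time rates assume a roughly constant hazard, so events concentrated soon after initiation would be diluted by long follow-up. They do not correct for calendar trends, or for the extra laboratory testing that follows therapy initiation (9.2), which can raise detection of laboratory-defined events under intervention. The SAP should state these limits.

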	mEq/L], hyperkalemia [K >5.5 mEq/L], AKI [defined as Cr increase >0.5 from baseline], Hyponatremia [Na<130 mg/dl], volume overload [urgent clinic visit/ ER visits for lower extremity edema, dyspnea, with clinical evaluation consistent with volume overload], hypotension (SBP <90mmHg), bradycardia (HR <50 bpm). Outcomes determined by review of medical, hospital, and billing records.
OTHER EVALUATIONS	None
SAFETY EVALUATIONS	Adverse events (to include hypokalemia [K<3.0 mEq/L], hyperkalemia [K >5.5 mEq/L], AKI [defined as Cr increase >0.5 from baseline], Hyponatremia [Na<130 mg/dl], volume overload [urgent clinic visit/ ER visits for lower extremity edema, dyspnea, with clinical evaluation consistent with volume overload], hypotension (SBP <90mmHg), bradycardia (HR <50 bpm).
PLANNED INTERIM ANALYSES	At 30-days after implementation for cluster 1, we will evaluate for safety. Serious adverse events will be monitored by the research team on an ongoing basis throughout the study.
STATISTICS Primary Analysis Plan	To assess the effectiveness of our intervention, measurement of rates of GDMT, including each specific medication of ACE inhibitors, ARB, ARNI, beta-blockers, MRA, SGLT2 inhibitors will be performed at baseline, at each cross-over time point, and at the conclusion of 6 months after the implementation of the intervention. The main analysis of our stepped wedge design will be based on a logistic mixed-effects model which will contain a random intercept to account for between-cluster variability, a fixed effect parameter for time, and a group indicator variable for the treatment for each subject and time to capture treatment differences over time.
Rationale for Number of Subjects	We anticipate there is approximately 100 patients with HFrEF actively engaged in care at GIMC. Our goal to enroll all patients given ethical concerns with withholding implementation to all patients.

SECTION 1: BACKGROUND

Statement of Purpose:

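### Section 11.3 leaves two candidate primary models unranked, and the one tied to the primary outcome lists no time term

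*Combined protocol and SAP*

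**What the plan says.** Section 11.3 contains two models.

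- **Logistic mixed model.** "The main analysis of our stepped wedge design will be based on a logistic mixed-effects model". It has "a random intercept to account for between-cluster variability, a fixed effect parameter for time", and a treatment indicator that varies by subject and time. The synopsis gives this model, and no other, in its Primary Analysis Plan entry.
- **Log-link GLM.** A later paragraph opens by tying the primary analysis to intention to treat and continues: "A generalized linear model will be used to assess the relationship between randomization cluster status and the primary outcome". Then: "The model will use a log-link and independent correlation structure to allow for calculation of adjusted risk ratios". The P<0.05 rule follows in the same paragraph, and the approach is extended: "For categorical secondary outcomes, a similar generalized linear modeling approach will be used".

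Neither model is called a sensitivity analysis. Section 11 promises a later SAP that may modify the plan.

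On the design, Section 4.4 says "Cluster 1 will have the model implemented at time 0, cluster 2 at 30 days", and so on in 30-day steps. Section 4.3 says "each patient cluster will begin the study as a control". Section 4.4 gives as one reason for the design that it allows the team to "evaluate the effect of secular trends towards better care over time". Section 7.3 gives all physicians a guideline lecture at the start, and Section 11.3 rates the risk of contamination as high.

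**The concern.** The two models differ in effect measure (odds ratio or risk ratio), in how they handle correlation, and in whether time is a term. Either could be reported as prespecified, and the choice could be made after the results are known.

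The missing time term matters most. Exposure is tied to calendar time by design, and the plan itself expects usual care to improve. A GLM with on/off status and no period term compares later intervention months with earlier control months, so it credits any usual-care rise to the intervention. That undoes the separation Section 4.4 gives as a reason for the design. The percentages on each drug class, as categorical secondary outcomes, inherit the same model.

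The exposure is also unclear. If cluster status means cluster number, the GLM has no treatment contrast at all, because every cluster receives the model.

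**Working it through.** **1. The plan's own power figure.** Section 11.4 states >95% power for 25% to 50%, with four clusters of 20 and five time points including one baseline. Assume a two-sided 5% test, a mean proportion of 0.375, period effects and no intra-cluster correlation:

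- Cell variance: 0.375 × 0.625 / 20 = 0.0117.
- Information: with t of 4 clusters on at time t, the sum of t(4 − t)/4 is 0 + 0.75 + 1 + 0.75 + 0 = 2.5.
- SE = √(0.0117/2.5) = 0.0685; 0.25/0.0685 − 1.96 = 1.69; power 95.5%.

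The figure reproduces. With an intra-cluster correlation of 0.05 it falls to 86.3%. With no time term, 200 v 200 independent observations give 99.95%. Both models therefore satisfy >95%, and Section 11.4 does not show which was meant.

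**2. How far apart in time the compared months lie.** Mean month from first measurement:

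- Section 4.4 schedule (5 clusters, months 0 to 4): on 40/15 = 2.67; control 10/10 = 1.00.
- The same with a pre-start baseline, as Section 4.3 implies: on 55/15 = 3.67; control 20/15 = 1.33.
- Section 11.4 layout: on 30/10 = 3.00; control 10/10 = 1.00.

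**3. Proportion on therapy, no true effect.** Take 25% at first measurement, rising d a month (assumed). The false risk ratio without a time term is (0.25 + d × mean on-month)/(0.25 + d × mean control month). On the Section 4.4 schedule at d = 0.05 this is 0.383/0.300 = 1.28. Type I error comes from simulation: 2,000 trials per setting, 20 patients per cluster, assumed within-patient latent correlation 0.8, patient-robust SEs.

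| Layout, no time term | 2 points/month | 3 points/month | 5 points/month |
|---|---|---|---|
| Section 4.4 schedule | RR 1.12, 11% | RR 1.18, 15% | RR 1.28, 34% |
| With pre-start baseline | RR 1.17, 21% | RR 1.24, 36% | RR 1.37, 74% |
| Section 11.4 layout | RR 1.15, 14% | RR 1.21, 25% | RR 1.33, 51% |

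With period effects, type I error is about 5 to 6% in all three layouts. With no trend, the time-free model gives 5% on the Section 4.4 schedule. On that schedule at 2 and 5 points, the time-free figures are 11% and 41% at correlation 0.5, and 8% and 29% with 80 patients. Repeat simulations agreed: 8 to 21% at 2 points and 34 to 74% at 5 points across the layouts, against 5 to 7% with period effects.

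**4. The increase endpoint of Section 5.1.** How a control period is scored is not defined. Assume a constant usual-care uptake u a month and no true effect (4,000 trials per setting, 100 patients, Section 4.4 schedule).

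- Scored within each 30-day window: median RR 1.00, type I error 2 to 5%. No bias.
- Scored against baseline: the chance of an increase by month j is 1 − (1 − u)^j. At u = 5% the averages are 0.1697 on and 0.0963 control, RR 1.76; at u = 2%, 0.0711/0.0394 = 1.80. For u = 2%, 3% and 5%, RR is 1.80, 1.79 and 1.76, and type I error 22%, 27% and 42%. Period effects in the GLM reduce this to 10.5%, 8% and 7%. It does not fully reach 5%, because events are sparse.

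**5. The mixed model already in the plan.** With a cluster intercept and categorical periods, type I error was 3 to 4% in simulation (2,000 trials per setting).

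**The case against.** The strongest reply is that the plan does signal a ranking. Section 11.3 calls the mixed model the main analysis, the synopsis lists only that model, and it has a time term. The bias needs the GLM to be primary, cluster status to mean on/off, and adjustment to exclude time; the documents state none of these. The two models may also be meant for different outcomes, since the mixed model is introduced after a sentence on GDMT rates.

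On size, the table in step 3 concerns the proportion on therapy, which reaches the GLM through the secondary outcomes. For the increase endpoint, within-window scoring, a natural reading of an outcome 30 days after implementation, gives no bias. The trends are assumed, and 5 points a month is 5 × 4 = 20 points over the Section 4.4 schedule, close to the whole 25-point planned effect. A later SAP could settle the matter.

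Much of this stands as a limit on size. The synopsis favours the mixed model, the false-positive rates are conditional, and the steepest ones need a steep trend. It does not remove the defect. The GLM is the model whose sentence names the primary outcome, nothing demotes it, and its adjustment variables are unnamed. If the models serve different outcomes, the primary outcome falls to the one with no listed time term. The SAP is only promised, so the present text is the prespecification.

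**Conclusion.** The concern holds, and the conflict must be settled before the data are analysed. That two unranked models can each be read as primary, and that the GLM lists no time term, follows from the text alone.

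The size depends on fitting the GLM with on/off status and no period term, and on an assumed trend and within-patient correlation. For the proportion on therapy at 2 to 5 points a month with 100 patients on the Section 4.4 schedule, type I error is 11% to 34%, and up to 74% with a pre-start baseline. For the increase endpoint it ranges from no inflation (within-window scoring) to 22% to 42% (scoring against baseline). Without a usual-care trend the proportion-on-therapy analysis shows no inflation, but the plan itself expects a trend.

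Period terms make the comparison within periods. They also absorb provider spillover, so they do not recover an uncontaminated effect.

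**What to change.** 1. Name one primary model and one effect measure for the primary outcome. The planned logistic mixed model is sufficient; a patient random effect there would gain efficiency but is not needed for validity.
2. Put categorical period effects and an on/off treatment indicator for each period in that model and in the categorical secondary analyses.
3. Label the other model a sensitivity analysis, with the same period terms and its adjustment variables listed.
4. State how a control period is scored for the increase endpoint.
5. If the independence GLM is kept as primary, add patient-clustered robust SEs or a within-patient working correlation, because Section 9.1.1 measures each patient repeatedly. With period effects but model-based SEs, type I error was 12 to 16% (11% at correlation 0.5).

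The cost is wording only, with no new data. Power for 25% to 50% on the Section 4.4 schedule, assumed correlation 0.8:

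| Model with period effects | 100 patients | 80 patients |
|---|---|---|
| Logistic mixed model | 98% | 95% |
| Log-link GLM, independence, robust SEs | 91% | 84% |
| Log-link GLM, exchangeable within patient | above 99% | above 99% |

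In Section 11.4's four-cluster layout the mixed model has 93 to 94% (correlations 0 to 0.8), slightly under the stated >95%, and the independence GLM has 82%. At correlation 0.5 on the Section 4.4 schedule, the independence GLM has 97% and 93%, and the exchangeable version 99% and 98%. Naming the mixed model therefore costs little.
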